# 1 Revisions

Version	Date	Reason
1.0	May 25, 2017	Version 1.0 developed prior to enrolling first patient in the trial.
1.1	September 19, 2017	Minor clarifications after feedback from clinicians.
1.2	December 4, 2018	Updated sample size.
1.3	June 19, 2022	Finalization of SAP prior to database lock.
1.4	August 30, 2023	Specification of post-hoc analysis to compute relative risks for binary endpoints (Section 7.1).
1.5	January 19, 2024	Specification of post-hoc analysis of limb symmetry index (Section 7.2).
1.6	April 8, 2024	Specification of changes to the SAP as a result of the review process.

## 3 Introduction

The treatment of proximal hamstring avulsions is controversial. The literature suggests that operative treatment is superior to conservative, non-operative management. However, randomized evidence is lacking. Moreover, few of the existing observational studies have used validated outcome measures, such as Harris Hip Score, the Lower Extremity Functional Scale (LEFS), or the Perth hamstring assessment tool (PHAT).

The Proximal Hamstring Avulsion Clinical Trial (PHACT; NCT03311997) is a prospective, preference tolerant, multicentre, randomised, controlled non-inferiority trial with the aim to provide reliable evidence on how to treat physically active patients, 30–70 years of age, with proximal hamstring avulsions.

The planned analyses identified in this statistical analysis plan (SAP) will be included in future manuscripts. Exploratory analyses not necessarily identified in this SAP may be performed to support planned analyses. Any post-hoc exploratory or unplanned analyses not specified in this SAP will be identified as such in manuscripts for publication, and added as addenda to the SAP. The SAP may be updated during the course of the trial but will be finalized before database lock or any comparative analyses. Any further future analyses not specified in the analysis protocol will be documented in the revision history of this document.

[figure not shown]
## 4 Trial overview

### 4.1 Trial design

Patients with proximal hamstring avulsion will be randomly assigned to either operative treatment or to non-operative treatment. Both groups will follow the same standardized rehabilitation protocol.

Patients who are eligible for trial participations but where the patient or the treating physician equipoise to treatment cannot be reached, will be asked to participate in a parallel observational follow-up cohort with identical treatment options and follow-up. In the parallel cohort, the patient's/surgeon's preferred treatment is provided. Patients are followed for 24 months with study visits at 3, 6, 12, and 24 months.

An overview of the trial design is shown in Figure 1. The study design, interventions, eligibility criteria, and conduct are outlined in detail in the study protocol.

**Figure 1.** Study design. Patients aged 30-70 years old with proximal hamstring avulsions who meet inclusion criteria and none of the exclusions criteria are invited for participation. IPAQ-SF, International Physical Activity Questionnaire Short Form; LEFS, Lower Extremity Functional Scale; PHAT, Perth hamstring assessment tool; RCT, Randomized Controlled Trial. Patients are followed for 24 months with study visits at 3, 6, 12, and 24 months.

## 4.2 Endpoints

### 4.2.1 Primary

The primary endpoint (measured at baseline, 3, 6, 12 and 24 months) is self-reported Perth hamstring assessment tool (PHAT). The primary analysis will be conducted using the measurement at 24 months.

### 4.2.2 Secondary

The secondary endpoints can be grouped into

- a) adverse events and complications (measured at 3, 6, 12 and 24 months)
- b) additional patient reported functional outcome scores (measured at baseline (if applicable), 3, 6, 12 and 24 month)
- c) physical performance-based tests (measured at 6, 12 and 24 months) including
  - c1) strength tests and
  - c2) functional tests
  - c3) range of motion
- e) imaging outcomes (measured at 24 month).

#### 4.2.2.1 Adverse events and complications (both groups)

- Surgical site infections (surgery group only)
- Neurological sequel
- Thromboembolic disease
- Re-rupture in surgically treated patients
- Other complications and reoperations

#### 4.2.2.2 Additional patient reported functional outcomes

- The lower extremity functional scale (LEFS; see protocol appendix LEFS).
- Self-reported pain score at rest, during sitting and during walking in the groups. This is a subset of the PHAT score (see protocol appendix PHAT).
- Patients reporting that they have returned to preinjury sporting activities (see protocol appendix return to sports).
- Visual Analogue Scale (VAS) satisfaction of treatment (see protocol appendix satisfaction).
- VAS self-reported recovery (see protocol appendix satisfaction).
- Activity level measured by IPAQ-SF preinjury level to follow-up (see protocol appendix IPAQ-SF).
- Time to return to work.

#### 4.2.2.3 Physical performance-based tests of both injured and uninjured leg.

##### Hamstring muscle strength

Maximum isometric force in supine position (see protocol appendices physio protocol and instruction). Study sites equipped with a computer-based isokinetic dynamometer will test maximum isokinetic force during knee flexion and hip extension (see protocol appendices physioprotocol and physioinstruction).

#### Functional tests

- Timed step test (see protocol appendices physio protocol and physio instruction) of the injured and uninjured side.
- Single leg hop tests (see protocol appendices physio protocol and physio instruction) of the injured and uninjured side.

#### Range of motion

Hip flexion and knee extension (see protocol appendices physio protocol and physio instruction)

#### 4.2.2.4 Radiological

- Hamstrings muscle volume and fatty infiltration in the injured and uninjured side measured by MRI at 24 months (see protocol appendix MRI protocol 24 months PHACT).
- Attached tendons at the ischial tuberosity measured by MRI at 24 months.

These endpoints are measured at 24 months.

### 4.3 Randomization and blinding

The REDCap (REDCap Software) randomization tool will be used to perform randomization of patients, which will be conducted using a random block size (2-6) stratified by study site.

To minimize ascertainment bias this trial is single-blinded, where the physiotherapist conducting strength and functional tests at 6, 12 and 24 months will be blinded to the intervention, by informing the patients not to tell what group they belong to and asking them to wear clothes concealing potential surgery scar. Statisticians analyzing the data will also be blinded to treatment arms. Consequently, analyses of adverse events will be conducted last (since these are likely to reveal group allocation). Similarly, results will be presented and discussed among investigators prior to analyzing and presenting adverse events (to preserve blinding as long as possible in the construction of the first manuscript from the trial).

### 4.4 Data management

All study data will be collected and managed in a digital case report form using REDCap electronic data capture tools hosted at Karolinska Institutet, Sweden. REDCap is a secure, web-based application supporting data capture for research studies.

Data will be kept securely in order to protect confidentiality before, during, and after the trial. A codebook matching the personal identification number and the trial identification number is kept at each study site and the trial identification number is noted in the patient's electronic medical chart. The study nurses and investigators can log on and enter data directly into the database. Patients will complete surveys at each visit. Any paper forms used are stored for cross-checking at each study site.

### 4.5 Trial reporting

The trial will be reported according to the principles of the CONSORT statements in scientific publications.

# 5 Analysis of the trial

## 5.1 Analysis populations

The *intention to treat (ITT) population* will consist of all participants randomized and consenting to be part of the study, irrespective of treatment received. Participants in the ITT population will be analyzed according to the treatment they are randomized to, regardless of whether they actually received this treatment or not.

We will also conduct *per-protocol (PP)* and *as-treated (AS)* analyses. Cases will be considered treatment crossovers if the randomly assigned treatment is changed. Non-operative treated patients who are treated operatively due to late complaints (>3 months after inclusion) will in PP and AS analyses be handled in two ways: (i) *not* considered crossovers, in which case we regard these sets of patients as a failed initial conservative treatment strategy, followed by surgery; (ii) considered as cross-overs (analogously to patients who switch groups early, i.e. within 3 months of randomization). The first definition will be employed in the main PP and AS analyzes, whereas the latter will be used in sensitivity analyses (see Section 5.8.4).

The *per protocol (PP) population* will be defined by the participants who were randomized to a specific treatment and received it according to the protocol. Analyses based on the PP population are based on post randomization events (treatment compliance vs. not), which may lead to biased results. We will therefore perform analyses on the PP population using inverse probability weighting to adjust for the effect of these post randomization events. Specifically, let  $A$  be an indicator variable that takes value 1 if the patient was randomized to the surgical arm and 0 if s/he was randomized to the conservative treatment arm. The conditional probability of adhering to the protocol given study arm and other covariates is  $Pr(P=1|Z,A)$ , where  $Z$  is patient covariates (age, sex, site, and degree of tendon retraction). Inverse probability weights of protocol adherence will be defined as  $W=1/Pr(P=1|Z,A)$ . The weights  $W$  will then be used to estimate the contrasts between the operative and non-operative arms using marginal models with a robust (sandwich) standard error estimator according to models specified in Sections 5.2 and 5.3.

The *as treated (AS) population* will be defined according to the treatment the patients actually received. Analogously to the PP population, the definition of the AS population is based on post randomization events, which may lead to biased results. We will therefore conduct analyses on the AS population by first identifying subgroups that are likely to require surgery and therefore should not be considered as good candidates for conservative treatment, and then contrast the outcomes of patients treated successfully in the conservative treatment arm with patients randomized to the surgery arm who similarly would not have crossed over had they been randomized to the conservative treatment arm. We will within the trial observe which patients in the conservative management arm who cross over. However, patients cannot cross over from the surgical to the conservative arm, after the surgery is performed. We will use matching based on inverse probability weighting (as defined above for the PP population) to identify a comparison group from the surgical arm for compliers in the conservative management arm.

The number and proportion of patients who did not receive the treatment they were allocated to will be reported. If any other trial treatment options were known to be received, instead of or in addition to, the allocated treatment during the follow-up period after the first randomization, these will be collected and reported.

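### SAP 5.1: the as-treated analysis targets patients who would not have crossed over from conservative care, but the per-protocol weights it borrows do not select them

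*SAP*

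**What the plan says.** All the relevant text is in SAP section 5.1.

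- **Per-protocol population:** "participants who were randomized to a specific treatment and received it according to the protocol". To offset selection after randomisation, the SAP says: "Inverse probability weights of protocol adherence will be defined as" W=1/Pr(P=1|Z,A). Here A is the randomised arm ("be an indicator variable that takes value 1 if the patient was randomized to the surgical arm and 0 if" conservative), and Z "is patient covariates (age, sex, site, and degree of tendon retraction").
- **As-treated population:** it "will be defined according to the treatment the patients actually received". The SAP then sets out a more specific plan. It first identifies subgroups likely to require surgery. It then aims to "contrast the outcomes of patients treated successfully in the conservative treatment arm" with those of "patients randomized to the surgery arm who similarly would not have crossed over had they been randomized to the conservative treatment arm".
- **Method for that contrast:** "We will use matching based on inverse probability weighting (as defined above for the PP population"), in order to find a surgical-arm comparison group for the conservative-arm compliers.

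No other weight, matching rule, cross-over model or subgroup cut-off is given for the as-treated analysis.

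**The concern.** The target group on the surgical side is defined by what would have happened under the other allocation. Selecting it needs the probability of not crossing over under conservative care, Pr(P=1|Z,A=0), evaluated for surgical-arm patients. For those patients W uses Pr(P=1|Z,A=1), the probability of adhering to surgery, which carries no information about cross-over from conservative care. In the conservative arm, W gives most weight to the compliers who most resemble cross-overs. That runs against the section's aim of setting aside poor candidates for conservative treatment.

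At stake is what the as-treated estimate describes. If W is used as written, a figure labelled as the effect in patients who can be kept on conservative care may describe a different population.

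**Working it through.** The SAP gives no cross-over rates and no figure that depends on this choice, so there is nothing of its own to reproduce. Step 1 is algebra from the SAP's definitions. The inputs to steps 2 to 4 are assumptions for illustration, apart from the SD, arm sizes and margin in step 4.

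**Step 1. Which population each weight represents.** Let p(Z) be the covariate density of the patients analysed.

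- Adherers in arm a have density proportional to p(Z)·Pr(P=1|Z,A=a). Multiplying by W=1/Pr(P=1|Z,A=a) gives p(Z) in both arms. This is the per-protocol contrast.
- The stated target has density proportional to p(Z)·Pr(P=1|Z,A=0). Conservative-arm compliers already have it with weight 1. Surgical-arm adherers reach it with weight Pr(P=1|Z,A=0)/Pr(P=1|Z,A=1). If all surgical-arm patients are kept, the weight is Pr(P=1|Z,A=0).

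**Step 2. Two equal strata (low and high retraction).** Assumed: conservative-arm adherence 0.95 (low) and h (high); surgical adherence 0.95 in both; conservative mean PHAT 80 and 65; effect = surgery minus conservative. The high-retraction share among compliers is s = h/(0.95+h). W in both arms gives each stratum weight 0.5.

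| h | Cross-over | s | W in both arms | Target, effects 0 and 10 (10s) | Target, effects 2 and 8 (2+6s) |
|---|---|---|---|---|---|
| 0.85 | 10% | 0.472 | 5.00 | 4.72 | 4.83 |
| 0.65 | 20% | 0.406 | 5.00 | 4.06 | 4.44 |
| 0.45 | 30% | 0.321 | 5.00 | 3.21 | 3.93 |

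With effects 0 and 10 the gap runs from 5.00 − 4.72 = 0.28 to 5.00 − 3.21 = 1.79. With effects 5 and 5, or equal adherence in both strata, W and the target agree at 5.00.

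*W on the surgical arm only* (h = 0.65, effects 0 and 10): the surgical mean is 0.5×80 + 0.5×75 = 77.50. The unweighted complier mean is 80 − 15×0.406 = 73.91. The difference is 3.59, against a target of 4.06. With a constant effect of 5, the surgical mean is 0.5×85 + 0.5×70 = 77.50, so the difference is again 3.59, now against 5.00. The shortfall arises because the arms differ on Z. These are plain weighted means.

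**Step 3. Continuous retraction.** Assumed: Z standard normal, Pr(no cross-over) = logit⁻¹(1.7 − 0.9Z), which gives 81% compliers, and effect 4 + gZ. Numerical integration gives a mean Z among compliers of −0.150, so the target is 4 − 0.150g.

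| g | W in both arms | Target | Gap |
|---|---|---|---|
| 1 | 4.00 | 3.85 | 0.15 |
| 2 | 4.00 | 3.70 | 0.30 |
| 4 | 4.00 | 3.40 | 0.60 |

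**Step 4. Scale.** The non-inferiority margin is 10 (section 5.2). With SD 20 (section 6.2), the standard error of a difference is 20√(2/60) = 3.65 with 60 per arm, or 20√(2/50) = 4.00 with 50. The gaps are below one standard error.

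**The case against.** A reader might go further and infer that the as-treated analysis is simply the per-protocol analysis run twice. The document does not support that. Section 5.1 first identifies subgroups likely to require surgery, and then speaks of matching to find a comparison group in the surgical arm. If subgroups are set aside, W restores the mix of those who remain, not of everyone randomised. In the step 3 model, dropping patients with predicted non-cross-over below 0.6 (7.5% of patients) moves the W result to 3.85 for g=1 and 3.39 for g=4, very near the targets of 3.85 and 3.40. The authors may also have meant to match on predicted Pr(P=1|Z,A=0), which the per-protocol adherence model can supply.

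This rules out the stronger reading but does not rescue the method. The near-agreement depends on the cut-off: 0.5 gives 3.93 and 3.72, and 0.7 gives 3.69 and 2.77. The SAP states no cut-off. Matching on Pr(P=1|Z,A=0) would be close to the target, but it is not the weight the cross-reference points to.

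Three further points stand:

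- The gaps are small and rest on assumed inputs.
- No decision rule uses the as-treated result. The primary analysis was ITT and became per-protocol under section 7.3. Nothing says the as-treated result will be offered as corroboration.
- If the as-treated contrast is also fitted with the covariate-adjusted models of sections 5.2 and 5.3, much of the imbalance under one-arm weighting would be removed. The population represented would still not be the stated one.

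**Conclusion.** The point holds as a mismatch between a stated target and the only weight given for it. That part is algebraic and needs no assumed figures. With W on adherers in both arms and no defined exclusion, the analysis returns the per-protocol contrast. With W on the surgical arm only, it leaves the arms unbalanced on Z. The subgroup and matching steps are too undefined to be relied on as a repair.

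With W in both arms, the error vanishes if the effect does not vary with Z or if conservative-arm adherence does not depend on Z. Otherwise it is about 0.15 to 1.8 PHAT points under the assumed 10% to 30% cross-over and assumed effect variation, against a margin of 10. The analysis is supportive, so the trial's main conclusion does not turn on this. What needs correcting is the definition and label of the as-treated estimate.

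**What to change.** In section 5.1, replace the parenthetical cross-reference to the per-protocol weights with weights specific to the as-treated analysis:

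1. Fit Pr(P=1|Z,A=0) in the conservative arm and predict it for surgical-arm patients.
2. Give conservative-arm compliers weight 1.
3. Weight surgical-arm adherers by Pr(P=1|Z,A=0)/Pr(P=1|Z,A=1). If all surgical-arm patients are kept, weight them by Pr(P=1|Z,A=0). State which set is used. Among adherers only, the simpler weight is biased when adherence to surgery depends on Z.
4. State the assumption that Z captures the common causes of cross-over and outcome.
5. Replace *treated successfully*, which could be read as selection on outcome, with *did not cross over*.
6. Reconcile this contrast with the section's opening definition by treatment actually received, and either define the subgroup and matching steps or remove them.

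The SAP is at version 1.6, after database lock, so this would be a documented post-hoc addendum. If the analysis has already been run with W in both arms and no exclusion, label the result an all-patient per-protocol-type estimate. The cost is one extra stated assumption and a small re-analysis, with no new data.

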## 5.2 Primary endpoint

PHAT scores (measured at 3, 6, 12, and 24 months) will be assessed and contrasted between the two treatment groups using a linear regression model that adjusts for an indicator of randomized treatment group assignment and for factors used to stratify randomization (site), age, sex, and degree of tendon retraction. The primary analysis will contrast the randomized groups at 24 months in the ITT population (analyses using other follow-up time points are specified in Section 5.8).

Based on the existing literature the standard deviation of PHAT measurements is ~16 – 21. The non-inferiority margin was set to half of the standard deviation (=10). The non-inferiority margin was agreed upon at a consensus group meeting that included orthopedic surgeons and statisticians. The one-sided alpha level will be 0.05. If conservative treatment is non-inferior on the one-sided 0.05 alpha level, we will repeat the test using a one-sided alpha of 0.025.

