### 5.5.2 Baseline characteristics

Baseline characteristics will be described descriptively and will include:

- Age
- Sex

- Injured leg
- BMI
- Occupational level
- Activity at injury
- PHAT
- LEFS
- IPAQ-SF
- Degree of tendon retraction
- Number of tendons detached (conjoint, semimembranosus or both)
- Time to treatment, (days)

Summary statistics will be used for each variable: median and interquartile ranges for continuous variables, and number and percentages for categorical variables.

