## 5.7 Missing data

All reasonable efforts will be taken to ensure that the level of missing data and loss to follow-up will be minimal.

Missing data can occur in different ways in the study: (1) individual questions in the instruments (e.g. the PHAT questionnaire) can be left unanswered; (2) data on specific endpoints may be entirely missing at different follow-up timepoints (due to a e.g. a functional test not being performed or data on a specific instrument not collected); and (3) patients can miss specific follow-up visits or drop out of the study altogether (resulting in no information on endpoint data for the corresponding follow-up timepoint or missing data on all subsequent follow-up timepoints).

Missing data on individual instrument (e.g. PHAT) questions will be imputed using predictive mean matching (PMM), with donor pool (k)=5.

Missed follow-up visit at specific follow-up timepoints will be handled using a multiple imputation by chained equations (MICE). The multiple imputation protocol will be based on models for predicting outcomes at specific follow-up timepoints based on outcomes data recorded at other time points together with treatment group, patient age, sex and degree of tendon retraction. For example, a missing PHAT score at 24 months will be imputed based on a regression model fit to

data from timepoints 3, 6, and 12 together with treatment group, patient age, sex and degree of tendon retraction.

We will generate 1,000 datasets with imputed outcome data, which will be analyzed separately. We will then use Rubin's rules to pool the estimated absolute differences in PHAT score and standard errors.

The global COVID pandemic has occurred during the conduct of this trial. COVID and restrictions have had a major impact on the healthcare situation and has resulted in rescheduled and cancelled follow-up visits in PHACT. Therefore, visits will be analyzed as follows:

- Visits occurring 2.5 to 4.5 months after randomization (or baseline for the observational cohort) will be considered as the 3 month visit.
- Visits occurring 4.5 to 9 months after randomization (or baseline for the observational cohort) will be considered as the 6 month visit.
- Visits occurring 9 to 18 months after randomization (or baseline for the observational cohort) will be considered as the 12 month visit.

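### Baseline PHAT is collected but used in neither the primary PHAT model nor the per-protocol weights; one labelled supportive analysis should add it to the outcome model

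*SAP*

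**What the plan says.** SAP 4.2.1 schedules the score before treatment as well as after: "The primary endpoint (measured at baseline, 3, 6, 12 and 24 months) is self-reported Perth hamstring assessment tool (PHAT"). Section 5.5.2 lists PHAT among the items covered by "Baseline characteristics will be described descriptively and will include".

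The primary model in 5.2 is a linear regression of PHAT that "adjusts for an indicator of randomized treatment group assignment and for factors used to stratify randomization (site), age, sex, and degree of tendon retraction". Baseline PHAT is not in that list. Section 5.1 builds the PP weights from "patient covariates (age, sex, site, and degree of tendon retraction") and then applies them to the models of 5.2 and 5.3, so baseline PHAT is absent at both steps of the PP analysis. The mixed model in 5.8.2 does not name it, and the beta regression in 5.8.5 keeps the primary covariates. No reason is given.

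Section 5.1 warns: "Analyses based on the PP population are based on post randomization events (treatment compliance vs. not), which may lead to biased results". Section 7.3 later makes PP the primary population without restating the model or the weight covariates. On crossovers, 5.1 offers two definitions, with and without operations for late complaints after 3 months, and says: "The first definition will be employed in the main PP and AS analyzes". That is the one that leaves late operations out, so in the main PP analysis only early switches count.

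**The concern.** A baseline measurement of the outcome is often one of its better predictors, and here it is already in the database. What its omission costs depends on the population.

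Under ITT, randomization protects the comparison. The estimate stays valid and only precision is lost.

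Under PP, patients who switched are removed, and the weights and the outcome model have to repair the imbalance that this creates. They can do so only for variables that they contain. If early switching depends on baseline PHAT, and baseline PHAT predicts 24-month PHAT beyond age, sex, site and retraction, the arms differ in a way that nothing corrects. Since 7.3 that affects the primary non-inferiority result.

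**Working it through.** **Inputs from the SAP (5.2 and 6.2).** Margin 10; SD 20; one-sided alpha 0.05, repeated at 0.025; 60 randomized and 50 required per arm.

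**Assumptions, none in the SAP.** The correlation *r* of baseline with 24-month PHAT given the other covariates; the early crossover rate *c*; the odds ratio (OR) of crossover per SD lower baseline PHAT. Higher PHAT is taken as better.

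**Check of the method.** Noncentral *t*, true difference 0, 60 per arm, SD 20, one-sided 0.05: power 85.9%, against 85% in Table 1 of section 6.2. All 12 rows of that table reproduce within 2 points. (The text there gives 85% power for 50 per arm, where this method gives 79.9%. That is a separate matter.)

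**Precision under ITT.** Adding baseline PHAT multiplies the residual SD by √(1 − r²) and uses one degree of freedom. At 50 per arm:

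| r | residual SD | power, 0.05 | power, 0.025 |
|---|---|---|---|
| not adjusted | 20.00 | 79.9% | 69.7% |
| 0.1 | 19.90 | 80.2% | 70.1% |
| 0.2 | 19.60 | 81.3% | 71.4% |
| 0.3 | 19.08 | 83.1% | 73.7% |
| 0.5 | 17.32 | 88.9% | 81.5% |

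At r = 0 the lost degree of freedom costs less than 0.01 percentage points of power.

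**Selection under PP.** Let crossover occur in the nonoperative arm only, by a logistic model in standardized baseline PHAT. The mean baseline among those who adhere then shifts upward by *s* SD, and

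- bias = 20 × r × s, in favour of the nonoperative arm;
- SE = 20 × √(1/60 + 1/(60(1 − c)));
- type I error = 1 − Φ(1.645 − bias/SE).

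| c | OR | s | SE | bias at r = 0.1 / 0.2 / 0.3 | type I error (%) |
|---|---|---|---|---|---|
| 5% | 1.5 | 0.020 | 3.70 | 0.04 / 0.08 / 0.12 | 5.1 / 5.2 / 5.3 |
| 5% | 2 | 0.034 | 3.70 | 0.07 / 0.14 / 0.20 | 5.2 / 5.4 / 5.6 |
| 10% | 1.5 | 0.040 | 3.75 | 0.08 / 0.16 / 0.24 | 5.2 / 5.5 / 5.7 |
| 10% | 2 | 0.066 | 3.75 | 0.13 / 0.26 / 0.40 | 5.4 / 5.8 / 6.2 |
| 20% | 1.5 | 0.079 | 3.87 | 0.16 / 0.32 / 0.47 | 5.4 / 5.9 / 6.4 |
| 20% | 2 | 0.129 | 3.87 | 0.26 / 0.52 / 0.77 | 5.7 / 6.5 / 7.4 |

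For example, at c = 20%, OR 2 and r = 0.3: 20 × 0.3 × 0.129 = 0.77; 0.77/3.87 = 0.20; 1 − Φ(1.445) = 7.4%. In 16 of the 18 cases the bias is below 0.5 points. At the repeat 0.025 test the error is 2.6% to 3.9%.

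**Other patterns.** If better-baseline patients cross over, the bias is −0.04 to −0.77 points and type I error 4.9% down to 3.3%. With c = 10%, OR 2 and r = 0.3, a further 10% of refusals in the surgical arm by worse-baseline patients cancels the bias (0.00 points, 5.0%). The same share by better-baseline patients raises it to 0.8 points (7.5%).

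**Where to put the covariate.** The weighted analysis of 5.1 was simulated with the true difference at the margin, sandwich errors, OR 2, r = 0.3 and 8,000 trials per setting (Monte Carlo SE about 0.04 points for bias and 0.25-0.3 percentage points for type I error):

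| Baseline PHAT in | bias at c = 5 / 10 / 20% | type I error (%) |
|---|---|---|
| neither (as written) | 0.19 / 0.38 / 0.77 | 5.6 / 6.1 / 7.4 |
| outcome model only | −0.02 / 0.02 / −0.01 | 4.9 / 5.2 / 5.0 |
| outcome model and weights | −0.02 / 0.01 / −0.01 | 4.8 / 5.1 / 5.2 |

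The SD of the estimate at c = 10% is 3.78, 3.63 and 3.65 in turn. Putting baseline PHAT in the weights raises the 95th percentile of the largest weight from 2.1 to 3.3 at c = 10% and from 2.6 to 4.7 at c = 20%. With five sites in the weight model and c = 20%, the share of trials with a weight above 5 rises from 1.2% to 8.2%.

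**The case against.** The omission is not an error or a contradiction. Nothing in the SAP promises baseline adjustment of PHAT, its covariate set is used consistently, and a prespecified model without a prognostic covariate is valid. The PP argument rests on three quantities that the SAP does not give. Nor does the SAP say whether baseline PHAT is a recalled pre-injury score or a post-injury score, which bears on whether it predicts 24-month PHAT or crossover at all. The illustrated bias is small beside a margin of 10. All of this stands. It makes the point an optional improvement and does not remove it, because the trial team holds the data that settle the question.

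Three stronger readings are tempting, and the SAP does not support them.

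- *The PP result is biased towards non-inferiority.* There is no such bias if crossover is unrelated to baseline PHAT, and other patterns reverse it. Section 5.1 says only that "patients cannot cross over from the surgical to the conservative arm, after the surgery is performed". That patients might decline before surgery is an inference, but it leaves room for exclusions in either arm.
- *The SAP is inconsistent because its propensity score includes baseline IPAQ.* That model, in the section on the observational cohort, describes treatment choice in an analysis that includes non-randomised patients. IPAQ measures activity, and baseline PHAT is missing there too.
- *Baseline PHAT belongs in the weights as well, at no cost.* In the simulation it gains nothing over the outcome-model term and enlarges the weights.

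**Conclusion.** The point holds as a modest improvement worth considering. Baseline PHAT is collected and enters neither the primary model nor the PP weights, and no named sensitivity model supplies it. For ITT the gain is precision only: 0.3 to 9.0 percentage points of power at one-sided 0.05 (80.2 − 79.9 and 88.9 − 79.9) for an assumed r of 0.1 to 0.5. For PP, an uncorrected selection is possible in the analysis that is now primary, with sign and size unknown. The illustrated 0.04 to 0.77 points and 5.1% to 7.4% hold only for crossover confined to the nonoperative arm, at 5-20%, with OR 1.5-2 and r 0.1-0.3. The top of that range needs all three assumptions at their upper end. The result for the outcome-model term alone further assumes a linear baseline effect that is equal in both arms. Nothing here shows that the reported conclusion is wrong.

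**What to change.** Results were known when section 7 was written, so leave the reported primary analysis as it is. Add to section 7 one analysis labelled post hoc and supportive: the 5.2 model with baseline PHAT as a linear covariate, reported for PP (with the 5.1 weights as written) and for ITT, beside the primary result.

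For this analysis, name baseline PHAT among the imputation predictors. The general rule in 5.7, "models for predicting outcomes at specific follow-up timepoints based on outcomes data recorded at other time points", can be read to include it, but the worked example there names only months 3, 6 and 12. State also how missing baseline scores are handled, and whether the score refers to before or after the injury.

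Do not add baseline PHAT to the weight model by default. At 10% crossover of 60 patients there are about 6 events to fit it.

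The cost is one degree of freedom and one further post-hoc model; no new data are needed.
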